4. ABBREVIATIONS

5. BACKGROUND AND RATIONALE

Sepsis is a common cause of serious illness and death with an estimated 123,000 cases and 46,000 deaths in the UK each year.¹ Similarly, high levels of sepsis have been reported internationally^{2,3} and sepsis is recognised by World Health Organisation as a global health priority.⁴ Many countries have nationwide sepsis action plans and all UK hospitals have set targets to rapidly diagnose and treat patients with sepsis. Timely appropriately targeted intravenous antibiotics have been shown to be effective in improving outcomes for patients, with a 4% increase in odds of mortality for every hour's delay in administration of intravenous antibiotics.^{5–7}

The need for rapid treatment has led to the development of clinical criteria and 'screening tools' have been proposed to identify patients with sepsis. These include Sequential (Sepsis related) Organ Failure assessment, Systemic Inflammatory Response Syndrome (SIRS) criteria⁸ and in England the National Early Warning Score (NEWS).⁹ NEWS2 is recommended by NICE and the Royal College of Physicians as the most effective screening tool for sepsis in the UK.^{10,11} Available tools are based on current observations which clinicians are able to take and quickly calculate a score but there is a paucity of evidence as to which tool to use and their effect on patient outcomes. Many of these have been embedded into electronic health systems which generate electronic alerts.

Potential pathways for the effectiveness of alerts when clinical deterioration is due to sepsis are likely to include an increase in the proportion of patients receiving intravenous antibiotics in one hour,¹² and other 'sepsis six' measures.¹³ Improved communication and changes in dialogue between healthcare teams has been suggested as an important pathway for improvements in clinical outcomes.¹⁴ In addition, the introduction of sepsis alerts is often accompanied by treatment plans as well as education and training activities. Little is known about the contribution of these and other potential mediators on the effectiveness of alerts.

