In order to identify the most effective digital alert for improving outcomes we will integrate findings from previous workstreams. WS4 will draw strongly on principles of systems modelling and the emerging field of causal inference epidemiology. Combining the results of the document analysis in WS1, the quantitative findings of WS2 and the qualitative findings of WS3 using a converging approach²⁷ the next step will be to assign causation. Directed Acyclic Graphs (DAGs)²⁸ are helpful in diagnosing sources of bias and helping investigators select a set of covariates that allow the estimation of causal effects from observed data. A workshop will be convened for this purpose. Using the results from WS1-3 and the conceptual framework (see Figure 1) a DAG will be produced to establish the causal pathways of the mechanism of action of the digital alerts.

Sampling Strategy

Not applicable for this part of the study.

Methods of Data Collection

This WorkStream will be based on the data collection from WS1-3

Methods of Data Analysis

We will use combined the results of WS1-3 using a converging approach and focussed workshops with Co-Investigators.

Study Sequence and Duration

WorkStream 4 will begin in January 2023 and be complete by July 2023.

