2.2 Participants

All adult (18+) inpatients admitted between 01/02/19 and 31/01/21 are initially eligible for inclusion in the study. We will liaise with data managers at each NHS Trust and identify all patients who triggered a sepsis alert in each Trust. The sample of patients included in the study are adult inpatients who triggered a sepsis alert at any point in their inpatient stay or time in A&E in the 24 months of the study.

The NHS Trusts included in the study are of differing sizes and may differ in case mix. In order to compare hospitals we will use patients with a serios infection, and therefore at risk of sepsis to adjust outcomes for patients with an alert. In order to identify patients with a serious infection will use the ICD-10 codes suggested by Inada-Kim et al and classed as 'Suspicion-of-Sepsis' (SoS). Patients are identified if a patient has an SoS ICD-10 code at discharge or at death.

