2.8 Missing data

Patient admissions will not be excluded if patient data is missing, an additional category of missing will be included for age, gender, ethnicity and deprivation. As part of quality checks, we will confirm whether there are any patterns in missing data, for example periods of time where no lactate were reported. Our experience of EHRs indicate that there can be periods of missing data relating to EHR downtime.

3. Statistical methods

(a) Describe all statistical methods, including those used to control for confounding

3.1 Differences in alerting over time and between patient subgroups.

We will describe the number of first alerts in each Trust in total and over different time periods. In order to compare between Trusts we will consider the number of available overnight beds as an indication of hospital size.[2]

In addition, we will compare the alerts in the ED compared to the number of consultants in the ED. We will use a Poisson model to determine if there are significant differences in alerts during different 'shifts' days of the week and seasons. The SoS admissions in the same period will be the offset in the Poisson model.

Differences in alert frequency in patient sub-groups will be assessed within and between NHS Trusts. We will use all patients discharged with an SoS diagnosis to adjust between hospitals as a case-mix adjustment.

We will describe differences in percentages of all patients and sub-groups of patients alerting between Trusts and assess the significances in differences using chi-squared tests. As there are many patient sub-groups and therefore multiple significance tests, we will use a p-value of 0.01 to assess significance. *3.2 Association between alerting and process measures*

Process measures for inclusion are IV antibiotics, blood samples taken for microbiology and lactate measurement. We will describe process measure completion in alerting patients across Trusts, and subgroups of patients including alert location, age-groups and other sub-groups. We will consider completion of individual process measures and completion of all three within three-hours.

We will model process measure completion using a logistic regression adjusted for confounding factors, primarily patient characteristics which have been identified by clinicians as clinically associated with non-completion of process measures.

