We will determine the association between the alert and completion of individual process measures, completion of the three measures, and whether the associations are different for different patient subgroups.

We will model each Trust separately and also model all patients in a multi-level model with clustering at Trust level. We will determine the sensitivity of results to the modelling approach.

Association between alerting and patient outcomes

We will assess the association between alerting and patient outcomes using a competing risks survival analysis with discharge and death as competing risks. This will allow us to fully adjust for patient factors and consider both patients who survive to discharge and those who do not. We will include process measure completion as time varying covariates.

In addition, we will separately model ICU admission after alerting using both a survival analysis and logistic model.

Association between alerting and coding

We will describe the coding of alerting patients between Trusts. The Trust which does not have a sepsis specific alert will be excluded. We determine if the differences are significant using chi-squared test. We will use descriptive approaches to compare sepsis coding between Trusts in patients with a SoS code. We will also consider whether the patterns are the same across the main patient subgroups. Statistical significance will be assessed using chi-squared tests.

(b) Methods used to examine subgroups and interactions

Within each model we will separately consider subgroups when we perform our analysis. We will consider a priori interactions.

(c) Missing data

Missing data will be included as a category on its own for factors such as ethnicity and deprivation. We will inspect data to identify periods of missing data which may be a result of EHR downtime, if necessary we will consider imputation.

We will ensure from clinicians that all process outcomes are likely to be recorded in the EHR and policy for carrying out the processes are the same across all Trusts.

Bibliography

[2] NHS Bed Availability and Occupancy Data – Overnight. Available from:

https://www.england.nhs.uk/statistics/statistical-work-areas/bed-availability-and-occupancy/bed-data-overnight/

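### The competing-risks model for alerting and outcomes adjusts for process measures that the protocol places on the alert's pathway, and no model without them is stated

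*Protocol*

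**What the plan says.** All of this is in the Protocol.

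- **The model.** In section 3 of the first Appendix study, the part that deals with outcomes after an alert reads: "We will assess the association between alerting and patient outcomes using a competing risks survival analysis with discharge and death as competing risks". The reason given is "This will allow us to fully adjust for patient factors and consider both patients who survive to discharge and those who do not". The next sentence is "We will include process measure completion as time varying covariates". No version without these covariates is stated, and the resulting coefficient is not described as a direct association.
- **The covariates.** Section 3.2 of the same study: "Process measures for inclusion are IV antibiotics, blood samples taken for microbiology and lactate measurement".
- **Their relation to the alert in the same Appendix.** The analysis just before this one treats the measures as something to be explained by the alert: "We will determine the association between the alert and completion of individual process measures, completion of the three measures".
- **Their place in the causal account.** Section 5, Background and rationale, says that the pathways by which alerts may work "are likely to include an increase in the proportion of patients receiving intravenous antibiotics in one hour", together with other sepsis six measures. It also mentions communication between teams, and treatment plans and training that accompany alerts.
- **The sample and exposure.** Section 2.2 of the first Appendix study takes adult inpatients who "triggered a sepsis alert at any point in their inpatient stay" or in A&E. Section 2.3 names the alert algorithm as the key exposure.
- **Mediation.** Objective 4.4 plans a mediation analysis in Workstream 4.

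**The concern.** The stated purpose of adjustment in this model is patient case mix. Antibiotics given, cultures taken and lactate measured in response to an alert are care, not case mix. If alerting, or one algorithm compared with another, is associated with better outcomes because patients are treated sooner, a model that holds treatment status fixed at each moment will not show that part of the association.

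What is left is not easily read as a direct association. The background to the first Appendix study notes that some alerting patients do not have sepsis and that process measures, IV antibiotics above all, will therefore not always be completed. Completion thus carries information on how ill the clinician believed the patient to be. If that severity is not fully captured by the patient factors in the model, conditioning on completion distorts the comparison.

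At stake is the reading of the planned outcome analysis of the first Appendix study. An algorithm that works through prompt treatment could look no different from one that does not. Workstream 4 combines the Workstream 2 findings to identify the most effective alert (objective 4.1).

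**Working it through.** The Protocol gives no effect size, event rate or power for this model, so there is no stated figure to reproduce. The check has two parts.

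**1. Are the covariates mediators by the Protocol's own account?**

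- Section 5 places IV antibiotics and other sepsis six measures between alert and outcome.
- Section 3.2 of the first Appendix study models completion of the same measures in association with the alert, including completion of all three within three hours.
- The outcome model then conditions on them.

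The measures are a response to the alert in one analysis and an adjustment variable for the alert in the next. Taking the algorithm as the exposure, as section 2.3 does, changes nothing: completion is still downstream of it. Lactate adds a complication. In Table 1 it is an input to the Red Flag and combination algorithms but not to NEWS or SJSA, so a lactate measurement can precede the alert in some Trusts and only follow it in others. The same covariate does not mean the same thing in each Trust.

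**2. How much can conditioning remove?** This is an illustration; every input is assumed and none comes from the Protocol.

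- 400,000 patients, half alerting, followed over 40 intervals.
- Process measure completed with probability 0.30 per interval after an alert and 0.05 otherwise.
- Death probability per interval = 0.004 × exp(d·A + b·M(t) + u·U), where A is the alert, M(t) is completion so far and U is a standard normal severity. Discharge competes at 0.02 per interval.
- Poisson model for the cause-specific death hazard, fitted without and with M(t).
- Share of the log hazard ratio removed = 1 − ln(HR with M) / ln(HR without M).

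| Scenario | d | b | HR without M(t) | HR with M(t) | Share removed |
|---|---|---|---|---|---|
| All through process measures | 0 | −0.7 | 0.731 | 0.974 | 1 − 0.0263/0.3133 = 0.92 |
| Mixed pathways | −0.15 | −0.5 | 0.698 | 0.873 | 1 − 0.1358/0.3595 = 0.62 |
| Mostly other pathways | −0.26 | −0.1 | 0.753 | 0.789 | 1 − 0.2370/0.2837 = 0.16 |

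In these three scenarios severity plays no part (u = 0), so the adjusted ratio should equal the direct effect exp(d): 1.00, 0.86 and 0.77. The fitted 0.974, 0.873 and 0.789 differ from these by simulation error. In the first row the true loss is therefore complete.

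A fourth scenario lets unmeasured severity raise both completion and death (coefficient 0.7 for each), with d = 0 and b = −0.7. The ratio is 0.767 without M(t) and 0.795 with it. The direct effect is exp(0) = 1.00 by construction, yet the adjusted model shows about 0.80. Here the adjusted coefficient is far from the direct effect it might be taken for.

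**The case against.** The strongest reply is that this study is not meant to estimate an effect. It is called mainly descriptive, its listed objectives concern the sample, frequency, timing and the Covid-19 period, and the model is said to assess an association. The impact of alerts is estimated elsewhere: by matching, regression adjustment and propensity methods in section 7.2, and by the controlled interrupted time series in the second Appendix study, whose listed confounders are age, sex, comorbidities, ethnicity and season. Neither plan lists process measures as adjustment variables. This stands, and it limits the point to one secondary analysis. It does not remove it, because a descriptive association between alerting and outcome is also changed by conditioning on what follows the alert.

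It is also fair to say that whether treatment completion is associated with outcome is a legitimate question, and that entering completion as time-varying is better than treating later care as known at admission. This too stands. It argues for reporting the process-adjusted model separately, not for making it the only one.

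Three stronger readings are tempting but not supported.

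- **Immortal time.** A reader might infer bias from alerting being defined over the whole stay. That needs a clock starting at admission and a non-alerting comparator. The Protocol states neither for this model, and the sample is described as alerting patients. The risk is open, not shown.
- **Order of work.** A reader might object that in Workstream 4 "a DAG will be produced to establish the causal pathways of the mechanism of action of the digital alerts" only after Workstream 2 is analysed. The diagram is to be built from the results of Workstreams 1 to 3, so drawing one earlier is a preference, not the correction of an error.
- **Borrowed size.** A reader might apply the 23% lower risk of death reported in the second Appendix study's background. That figure concerns the introduction of alerts at one Trust under a phased rollout, which is a different contrast from this model's.

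**Conclusion.** The point holds in a limited form. As written, the only competing-risks model for alerting and outcomes conditions on measures that the Protocol treats as consequences of the alert and as part of how it works. Its alert or algorithm coefficient is neither the total association nor a clean direct one.

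A reader might infer that the model removes the whole association. The Protocol does not support that: section 5 also names communication, treatment plans and training, and these are not adjusted for. What is lost is the part running through IV antibiotics, blood samples and lactate. Its size cannot be derived from the Protocol. The assumed scenarios run from about a sixth of the log hazard ratio to essentially all of it, and they show the range of possibilities, not a forecast.

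The conclusion rests on the measures responding to the alert, which the Protocol itself says. The further claim, that the remaining coefficient is not a clean direct association, rests on completion depending on severity beyond the adjusted patient factors. The Appendix makes that likely but does not establish it.

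**What to change.** In the first Appendix study, section on alerting and patient outcomes:

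1. Make the main competing-risks model one with baseline (pre-alert) patient factors only.
2. Report the model with time-varying process measures separately, labelled exploratory and linked to the mediation analysis of objective 4.4. State that it assumes no unmeasured confounding between process completion and outcome.
3. State what alerting is compared with, and the time origin. If non-alerting patients, for example those with a Suspicion of Sepsis code, are comparators, enter the alert as a time-dependent exposure. If only alerting patients are compared, start the clock at the alert.

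The cost is a change of wording and code, and one more model to fit and report. The within-three-hours measures in Table 2 already call for alert and process times, so no new kind of data item is implied. Whether those times have been extracted is not stated.

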1.1 Background/rationale

To improve care for patients with sepsis, comply with national financial incentive programmes, and make best use of the introduction of electronic health records hospitals in England have introduced digital sepsis alerts. A variety of algorithms have been used, with different workflows and with different implementation strategies.

A variety of studies have demonstrated that digital sepsis alerts, and more general deteriorating early warning scores such as NEWS2, have high predictive power for mortality.[1] A small number of studies have shown that introducing digital alerts to identify patients at risk of deterioration have had an impact on patient outcomes.[2-3]

Although randomised control trials are considered the gold standard for evidence, digital alerts have generally been introduced across hospitals without randomisation or phased across the hospital. In ICHT sepsis alerts were introduced in a phased approach and we used a propensity score based causal inference method (inverse probability of treatment weighting), common in the analysis of natural experiments, to emulate as much as possible a RCT using real world healthcare data. In ICHT the introduction of digital sepsis alerts was associated with a 23% lower risk of death within 30 days.[4]

In this study we aim to analyse the impact of the introduction digital alerts across five NHS Trusts. With the exception of ICHT the introduction of alerts was part of the introduction of electronic health records (EHR). This presents challenges, for example:

- Data availability prior to the introduction of EHRs is limited to data routinely collected for administrative purposes. This includes admission, discharge and formal diagnosis information, but excludes detailed microbiology information and detailed patient treatment information such as the administration of antibiotics.
- The impact of the alerts on patient outcomes will be confounded by the introduction of EHRs, a major change in the hospital system.

Although we would expect digital sepsis alerts to have the main impact on patients with sepsis, and this is the stated aim of many commercial sepsis alerts, administrative data may not be sufficient to identify patients with sepsis, particularly as national guidance on sepsis coding changed in 2014, effectively increasing the number of patients with an official diagnosis of sepsis.[5] In addition, efficient clinical response to digital sepsis alerts may result in a decrease in disease progression to sepsis. We have therefore decided to focus on outcomes of patients with an ICD-10 Suspicion of Sepsis code.[6] We will use interrupted time series with a control to determine the impact of the introduction of alerts on patient outcomes and process measures. Interrupted time series is an important methodology which allows

before and after comparisons whilst taking trends prior to the intervention into account and is considered a robust methodology for analysing natural experiments. However, confounding due to other 'interventions' occurring at the same time as the intervention of interest can confound interpretation. A control is an appropriate method to take this type of confounding into account.[7]

For the control we have selected patients with an ICD-10 code included in the category gastrointestinal bleeding. This is a suitable control as we would not expect these patients to trigger a sepsis alert and outcomes should not be impacted by patients being identified as having sepsis. The ICD-10 codes included in this indicator are shown in Table 1.

Objective - Quantify the impact of a digital alert on the key patient outcomes and process outcomes

Primary outcome: in-hospital mortality within 30 days

Secondary outcome: length of stay

ICU admission

2.Methods

2.1Study design

Setting - Describe the setting, locations, and relevant dates, including periods of recruitment, exposure, follow-up, and data collection

This is a time series analysis across five NHS Trusts in England and one NHS Trust in Wales. The period of study is 1st April 2010 to 31st March 2021.

2.2 Participants - the eligibility criteria, and the sources and methods of selection of participants All adult (18+) inpatients admitted as emergency patients between 01/04/10 and 31/03/2 are initially eligible for inclusion in the study.

Intervention group: patients with a discharge diagnosis including one of the SoS sepsis codes at any place in the diagnosis.

Control group: patients with a discharge diagnosis which is use by the NHS to identify patients with a 'Fall' code.

2.3 Variables - Clearly define all outcomes, exposures, predictors, potential confounders, and effect modifiers. Give diagnostic criteria, if applicable

Primary outcome: in-hospital mortality within 30 days of admission **Secondary**:

- In-hospital mortality within 7 days of admission
- Length of stay
- ICU admission

Intervention: Introduction of digital alerts or changes in screening programmes

Potential confounders:

- Age
- Sex
- · Comorbidities which increase the risk of poor patient outcomes
- Ethnicity
- Season

Sub-group analysis

Age-groups

Patients who are immune-compromised

2.4 Data sources/ measurement - For each variable of interest, give sources of data and details of methods of assessment (measurement).

Data are routinely collected data to comply with NHS requirements for Secondary Users Service. Data is quality checked by individual Trust before it is submitted to the NHS, and is compiled into Hospital Episode Statistics which have been widely used for research in the UK.

As part of the NIHR-Health Informatics Collaborative data managers at each trust shared data through a secure data platform. All data was quality checked and processed by the data warehouse team at ICHT.

Bias - Describe any efforts to address potential sources of bias

We are using a control intervention group to address the main source of bias – that is that for four of the six Trusts alerts were introduced at the same time as digital alerts.

Study size

Six NHS Trusts were recruited to take part in the study. The number of patients included in the study is determined by the number of patients who were discharged with an SoS ICD-10 code. The power to detect differences will be determined post-hoc.

Quantitative variables - Explain how quantitative variables were handled in the analyses. If applicable, describe which groupings were chosen and why

Ethnicity – ethnicity coding is based on recorded ethnicity using NHS ethnicity codes. Due to small groups of some ethnic groups we will combine into standard combinations for statistical comparisons. Full details of ethnic groups are included in the supplementary materials.

Age – We broke age into 10-year age groups. For statistical comparisons we combined smaller groups. Full details are included in the supplementary materials.

Length of stay - length of stay, measured in hours, was determined from the date and time of admission and discharge recorded in the patient record. For this descriptive study we will quantify length of stay for patients who are discharged alive.

Mortality – mortality was based on discharge destination recorded. For the purposes of this study only inhospital mortality was available for all NHS trusts.

Missing data

Patient admissions will not be excluded if patient data is missing, an additional category of missing will be included for age, gender, ethnicity and deprivation. As part of quality checks we will confirm whether there are any patterns in missing data.

Statistical methods

(a) Describe all statistical methods, including those used to control for confounding

Descriptive analysis

We will describe trends in patient mix over time using graphical methods, we will use time series to determine if there were changes in patient mix, including sub-groups of patients, patients with SoS and falls patients.

We will use break point approaches to identify potential key points in time where changes occurred. This will aid in interpretation of results.

Comparative analysis

We will use interrupted time series with a control, adjusted for patient case mix and season. Each Trust will be modelled separately as the introduction of sepsis alerts and electronic health records is different for each Trust. Comparisons will be made between the change in slope and step change in counts.

(b) Describe any methods which will be used to examine subgroups and interactions

Within each model we will separately consider subgroups when we perform our analysis. We will consider a priori interactions.

(c) Explain how missing data will addressed

Missing data will be included as a category on its own for factors such as ethnicity and deprivation. We will inspect data to identify periods of missing data, and consider imputation.

ICD-10 Code	ICD-10 Description
1850	Oesophageal varices with bleeding
K226	Gastro-oesophageal laceration - haemorrhage syndrome K228 Other specified diseases of oesophagus
K250	Gastric ulcer, acute with haemorrhage
K252	Gastric ulcer, acute with both haemorrhage and perforation
K254	Gastric ulcer, chronic or unspecified with haemorrhage K256 Chronic or unspecified Gastric ulcer with both haemorrage and perforation
K260	K260 Duodenal ulcer, acute with haemorrhage
K262	K262 Duodenal ulcer, acute with both haemorrhage and perforation

